7.1 Study timeline

Deliverables/Activities	2019											
	Jan	Feb	Mar	Apr	May	Jun	Jul	Aug	Sep	Oct	Nov	Dec
1. Study protocol												
Discuss study design with A&T	x	x	x									
Prepare study protocol			x	x	x	x						
2. Baseline data collection tools												
Develop questionnaires/data collection tools				x	x	x						
Select and contract survey firm					x	x						
Translate questionnaire							x					
Program CAPI questionnaire							x	x				
3. Local and US-based IRB approvals												
IRB application at IFPRI								x				
IRB application in Ethiopia							x					
4. Baseline survey implementation												
Pretest, revise and finalize questionnaire								x				
Enumerator training									x			
Data collection										x	x	
5. Data cleaning and analyses												
Data cleaning											x	x
Data analyses												x

Deliverables/Activities	2020											
	Jan	Feb	Mar	Apr	May	Jun	Jul	Aug	Sep	Oct	Nov	Dec
Data analyses	x	x										
6. Baseline results tables and datasets												
Draft and finalize baseline results			x	x	x	x						
Prepare clean datasets							x					

Deliverables/Activities	2021											
	Jan	Feb	Mar	Apr	May	Jun	Jul	Aug	Sep	Oct	Nov	Dec
7. Endline data collection tools												
Develop questionnaires/data collection tools				x	x							
Translate questionnaire						x						
Program CAPI questionnaire						x	x					
8. Local and US-based IRB approvals												
Obtain IFPRI IRB approvals to conduct fieldwork							x					
Obtain local IRB approvals to conduct fieldwork							x					
8. Endline survey implementation												
Pretest, revise and finalize questionnaire							x					
Enumerator training							x					
Data collection							x	x	x			
9. Data cleaning and analysis												
Data cleaning									x	x		
Data analyses										x	x	x
10. Endline results tables and datasets												
Draft endline results											x	x
Finalize endline report and findings												
Prepare clean datasets												

Deliverables/Activities	2022											
	Jan	Feb	Mar	Apr	May	Jun	Jul	Aug	Sep	Oct	Nov	Dec
9. Data cleaning and analysis												
Data cleaning												
Data analyses	x	x										
10. Endline results tables and datasets												
Draft endline results												
Finalize endline report and findings	x	x	x									
Prepare clean datasets				x								

References

**ALIVE & THRIVE ETHIOPIA (A&T-ETHIOPIA)
MATERNAL NUTRITION IMPLEMENTATION RESEARCH (MNIR)**

**A Feasibility Study of Integrating a Package of Maternal Nutrition Interventions into Antenatal Care
Services in Ethiopia: A Cluster-Randomized Evaluation**

Data Analysis Plan

Prepared by:

[name], [name], [name], and [name]

International Food Policy Research Institute

Final version date: August 11, 2021

Trial registration number: ClinicalTrials.gov NCT04125368

Study protocol: Impact evaluation study protocol, version 2, dated June 2, 2021

Acknowledgements: This data analysis plan was prepared before commencing any analysis with the impact evaluation endline survey data. All final decisions on the statistical analyses remain with the evaluation team.

I. Study Background and Approach

In Ethiopia, Alive & Thrive (A&T) has developed and integrated a package of maternal nutrition interventions as part of the antenatal care (ANC) services provided by the government health system. Interventions are implemented in seven woredas (districts) in two regions – SNNP (4 woredas) and Somali (3 woredas). Key interventions include (1) maternal nutrition counseling (on diet quality and quantity), (2) iron and folic acid (IFA) supplementation (adequate supply and counseling), (3) weight gain monitoring (measurement and counseling), and (4) counseling on early initiation and exclusive breastfeeding practices. The interventions align with the 2016 WHO ANC guidelines (World Health Organization, 2016) and aims of the National Nutrition Program (NNP II).

1.1 Research questions

The implementation research study addresses three research questions:

Research question 1 (RQ1)	What are the program impacts on maternal practices : (1) consumption of diversified foods during pregnancy; (2) consumption of IFA supplements during pregnancy; and (3) early breastfeeding practices?
Research question 2 (RQ2)	Can the coverage and utilization of key maternal nutrition interventions [mentioned above] during ANC be improved through system strengthening approaches?
Research question 3 (RQ3)	What factors influenced integration and strengthening of maternal nutrition interventions into the government ANC service delivery platform?

1.2 Impact evaluation study design

The impact evaluation of A&T's interventions used a cluster-randomized design with repeated cross-sectional surveys at baseline and endline. We applied stratified random allocation to 30 health centers within seven woredas, which were assigned to either the A&T intervention (15 health centers) or control areas (15 health centers). A small baseline survey was conducted in October-November 2019 and the endline survey was conducted in August-September 2021 in the same 30 health center catchment areas, thereby creating panel data at the health facility level (not at individual level). Program implementation faced major disruptions and was paused between April and September 2020 due to the COVID-19 pandemic and related state-level restrictions. Refresher training and support for implementation of interventions were reengaged starting October 2020, for full implementation duration of approximately 10 months.

1.3 Study sample

The two main study sample groups are: 1) pregnant women (PW), as this sample allows the assessment of dietary diversity; and 2) recently delivered women (RDW) who have children less than 6 months of age, as this sample provides the best opportunity to assess the outcomes related to intervention exposure throughout pregnancy. PW and RDW were sampled separately but within the same health center catchment areas. For PW, we estimated a total sample size of 540 women (270 per arm) will detect a difference of 0.6 food groups in the mean dietary diversity score. For RDW, we estimated a total sample of 1890 women (945 per arm) to detect a difference of 13 tablets in the mean IFA tablets consumed after intervention.

Additionally, we included husbands of RDW present at the time of the survey. Outside of the two main sample groups, nurses-midwives (1 per health center) and health extension workers (HEW, 1 per health

post with up to 3 health posts¹) were interviewed. At endline, direct observations of ANC visits (2 per health center and 1 per health post) to assess service quality, followed by exit interviews to assess service recall and satisfaction, were conducted among pregnant women attending ANC at the time of the survey.

Table 1: Expected sample sizes

Survey respondent type		Baseline 2019		Endline 2021	
		Intervention	Control	Intervention	Control
Household survey:					
1	Pregnant women	90	90	270	270
2	Recently delivered women (RDW) with children <6 months	180	180	945	945
3	Husbands of RDW	180	180	945	945
Service provider survey:					
4	Nurses-midwives (at health centers, HC)	15	15	15	15
5	Health extension workers (at health posts, HP)	45	45	45	45
Observations:					
6	ANC observation + exit interview (2 per HC, 1 per HP)	75	75
Total:		510	510	2,295	2,295

II. Outcome Measures and Indicators

Outcome measures corresponding to the three research questions are presented below. Only some outcome measures under RQ 1 pertain to the primary outcomes of the evaluation (i.e., used to test study hypotheses and arrive at a decision on overall study impact and to serve as basis to calculate the sample size); RQs 2 and 3 focus on secondary outcomes.

2.1. Research question 1 (impact on maternal nutrition practices)

For impact estimates, outcome measures related to maternal dietary diversity will be used from the PW dataset, and outcomes to IFA consumption and early breastfeeding practices will be used from the RDW data.

Table 2: Outcome measures for RQ1

Outcome	Indicator	Data source
Maternal dietary diversity	Primary outcome: - Dietary diversity score (# of food groups) Secondary outcomes: - % PW consumed at least 5 food groups (minimum dietary diversity)	PW survey
IFA consumption	Primary outcome: - # of IFA tablets consumed Secondary outcomes: - % RDW consumed 90+ IFA tablets - # of IFA tablets received	RDW survey

¹ Primary health care is provided at primary hospitals, local health centers and rural health posts. One or more health centers/primary hospitals exist at the *woreda* (district) level. Within each health center catchment area, there are multiple health posts, usually one per *kebele* (ward/subdistrict) level.

Early breastfeeding practices	Secondary outcomes: - % infants <6 months breastfed within 1h of birth - % infants <6 months with no pre-lacteals fed - % infants <6 months exclusively breastfed	RDW survey
-------------------------------	---	------------

2.2 Research question 2 (coverage and utilization)

For effects on coverage and utilization of interventions during ANC visits, outcome measures will be used from the RDW survey data. In the context of the overall evaluation, outcomes under this research question are considered as secondary outcomes.

Table 3: Outcome measures for RQ2

Outcome	Indicator	Data source
ANC visits and contacts	- # of ANC visits (at health facility) - % RDW with at least 4 ANC visits - % RDW received ANC visit in first trimester of pregnancy - # of contacts outside of health facility (home visits and women’s group meetings)	RDW survey
Counseling on dietary diversity and adequate intake	During ANC visits and other ANC contacts: - % RDW received counseling on maternal nutrition - % RDW received counseling on dietary diversity - % RDW received counseling on consuming adequate quantity of food	RDW survey
Counseling on IFA supplementation	During ANC visits and other ANC contacts: - % RDW received counseling on importance of IFA - % RDW received counseling on how/reminders to take IFA - % RDW received counseling on managing IFA side effects	RDW survey
Weight gain monitoring and counseling	During ANC visits and other ANC contacts: - # times weighed - % RDW weighted at least 4+ times/at each ANC visit - % RDW received counseling about weight gain during pregnancy	RDW survey
Counseling on early breastfeeding practices	During ANC visits and other ANC contacts: - % RDW received counseling on breastfeeding practices - % RDW received counseling on early initiation of breastfeeding - % RDW received counseling on not feeding pre-lacteals - % RDW received counseling on exclusive breastfeeding	RDW survey

2.3 Research question 3 (health system factors)

For assessing factors related to strengthening service delivery, measures will be used from the health facility checklist (health centers and posts) and N-M and HEW datasets. In the context of the overall evaluation, outcomes under this RQ3 count as secondary outcomes.

Table 4: Outcome measures for RQ3

Outcome	Indicator	Data source
Equipment and materials to support maternal nutrition services	- % HC/HP with maternal nutrition counseling job aids - % HC/HP with IFA supplementation job aid - % HC/HP with breastfeeding counseling job aids - % HC/HP with functional weighing scale - % HC/HP with currently stocked with IFA tablets - % HC/HP with register to monitor IFA stocks - % HC/HP reporting stock-out of IFA in past 6 months	Health facility checklist

Service providers' training and supportive supervision	
 - % NM/HEW received maternal nutrition training - % NM/HEW by training content - % NM/HEW received ANC supervision - % NM/HEW by supervision content 	N-M survey HEW survey
Service providers' knowledge	
 - Knowledge scores for dietary diversity, adequate intake, IFA, and weight gain monitoring - Knowledge scores for breastfeeding 	N-M survey HEW survey
Service providers' work tasks and workload perceptions	
 - % NM/HEW record-keeping on ANC services - % NM/HEW by content of record-keeping - % NM/HEW with increased workload in past 1y due to ANC services 	N-M survey HEW survey
Service providers' provision of services	
 - % NM/HEW provided maternal nutrition interventions - % NM/HEW by counseling messages provided (on dietary diversity, IFA, weight gain monitoring, and breastfeeding) - % NM/HEW used job aids for maternal nutrition counseling - % HEW provided home visits to PW/number of visits in last 3 months - % HEW conducted PW conference/number of meetings in last 3 months 	N-M survey HEW survey

III. Statistical Analysis Plan

3.1 General principles and methods

Data analyses will be performed using STATA version 16.0 (StataCorp LLC). All applicable statistical tests will be two-sided to allow potential findings of unexpected effects. Statistical significance will be presented at levels of $p < 0.05$, $p < 0.01$, and $p < 0.001$.

A diagram presenting the flow of clusters and individuals through the trial, based on the Consolidation Standard of Reporting Trials (CONSORT) statement: extension to cluster randomized trials (Campbell et al., 2012; Eldridge et al., 2016), is shown as follows.

[figure not shown]

Figure 1. CONSORT flow diagram for repeated cross-sectional surveys

3.2 Sample characteristics

Baseline and endline characteristics will be reported between randomized program groups (A&T and control). For household samples, indicators of maternal characteristics (age, marital status, education, occupation, and religion), obstetric history (age of marriage, age at first birth, gravida, parity, number of living children, and trimester of pregnancy), household composition (size, number of adults and children, and household head) and other household characteristics (household food security, livelihood, and socioeconomic status) will be reported. Binary variables will be summarized as proportions, and continuous variables will be summarized as mean values with standard deviations (when normally distributed) or as median with interquartile range (for non-normal distribution variables). T-test will be used to compare and infer significant difference between the program groups by survey round.

Table 5: Dummy table for sample characteristics

Indicator	Baseline	Endline
-----------	----------	---------

	A&T (N=)	Control (N=)	A&T (N=)	Control (N=)
	Mean (SD)	Mean (SD)	Mean (SD)	Mean (SD)
Age of respondent (years)				
	Percent	Percent	Percent	Percent
Marital status Education level Occupation Religion				

*p<0.05, **p<0.01, ***p<0.001

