For the sample size for recently delivered women, we used the number of IFA tablets consumed from the DHS 2016 data for SNNPR (mean: 33.19, SD: 30.36), assuming an ICC of 0.15. We calculated that a sample of 945 recently delivered women per group will be able to detect a difference of 13 tablets consumed. For the proportion of women who consumed 90+ IFA tablets, we calculated that a sample of 450 recently delivered women will be able to detect a minimum of 15% increase in women consuming 90+ IFA tablets. At baseline, an error in the final Computer-Assisted Personal Interviews (CAPI) form for recently delivered women led to missing data values for the outcome variable on total IFA tablets consumed. We instead used the percentage of recently delivered women at baseline who ever consumed IFA tablets (84.3 %) and assumed an ICC of 0.150. We estimate that the sample size will detect a 12.3% increase in women who ever consumed IFA tablets. If husbands of recently delivered women are present at the time of the endline survey, they will also be interviewed briefly about their exposure to interventions, health and nutrition knowledge and any support provided during pregnancy.

Nurse-midwives and HEWs providing ANC in the study areas will also be included in both baseline and endline surveys. Three kebeles/health posts (where HEWs fall under the supervision of corresponding health centers) will be sampled per health center catchment area. Government guidelines advise that pregnant women should receive their first and last ANC visits at the health center, and other ANC visits may be provided at health posts. Direct observations of ANC visits (two per health center and one per health post) to assess service quality, followed by exit interviews to assess client satisfaction, will be conducted at endline among a subgroup of pregnant women attending ANC at the time of the survey.

At baseline, a light data collection at all facility levels (health centers and health posts) and subsamples of pregnant and recently delivered women will be conducted to assess comparability between study arms. At endline, the full samples of pregnant and recently delivered women will be surveyed.

Thus, the overall study samples sizes are presented in **Table 3**.

Table 3. Sample sizes

	Baseline 2019		Endline 2020	
	Intervention	Control	Intervention	Control
Pregnant women	90	90	270	270
Recently delivered women/Husbands	180	180	945	945
Nurse-midwives (1 per health center)	15	15	15	15

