3.1 Allocation

A cluster is defined as the health center catchment area. Four woredas in SNNPR (with 18 health centers and 2 hospitals) and two woredas in Somali region (with 10 health centers) were selected as intervention areas (see **Figure 3**). The samples across the two regions will be pooled to estimate effects at program level. We will use stratified randomization to try to balance potential co-interventions and confounders. Where there are odd numbers of health centers within woredas, the remaining health centers will be randomized within the same region. Then, 15 clusters will be allocated to the intervention arm and 15 clusters will be allocated to the control arm by use of computer generated pseudo-random numbers.

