4.4 Statistical methods

Data analysis will use econometric analysis to control for (any) differences at baseline and between intervention and comparison groups for all relevant variables of interest. Statistical testing for differences between the two groups will be done using a random effects regression, accounting for the clustering of errors within and across health center catchment areas.

The randomized study design allows for the identification of causal effects of the maternal nutrition intervention through comparisons of mean outcomes between the treatment and control groups. Key indicators will include dietary diversity (among pregnant women), IFA consumption, weight gain monitoring, and breastfeeding practices (early initiation and exclusive breastfeeding). Impacts will be assessed using “difference-in-difference” (DID) estimation and/or analysis of covariance (ANCOVA) controlling for covariates. Data management, data cleaning and statistical analyses will be conducted using Stata version 16 (Statacorp, USA). The statistical significance for tests will be set at 5% for main effects or 10% in case of interactions. All statistical tests will be one-sided.

V. Methods: Monitoring

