3.3 Impact estimates

The main analysis of impacts will be performed using intent-to-treat (ITT) specifications, wherein all study participants in the originally assigned program group at baseline are included in the statistical analysis and analyzed according to their program group, regardless of whether they received interventions or not. Women who refused or withdrew consent or those who are ineligible according to study protocol are excluded from ITT analysis.

The main impacts of the interventions will be estimated for: (1) dietary diversity score, (2) consumption of IFA supplements, and (3) early breastfeeding practices; secondarily, impact will be estimated for exposure to key interventions: (4) maternal nutrition counseling, (5) counseling on IFA supplementation, (6) weight gain monitoring and counseling, (7) breastfeeding counseling. The impact on dietary diversity will be assessed among PW, and impact on all the remaining outcomes will be assessed among RDW.

Given that the main impact indicators with full sample sizes are collected at endline only, ITT linear regression models will be used to test the means of the outcome for estimates of group differences (intervention vs. control) at endline, with standard errors clustered at the health center level. In the ITT adjusted models, we will control for gestational age (for PW only), maternal characteristics, child age and sex (for RDW only), and other variables that may be different between study arms. Robustness tests will be conducted using difference-in-difference analysis where outcome variables exist at baseline.

Table 6: Dummy table for impact estimates

Indicator	Baseline		Endline		Unadjusted impact est.¹	Adjusted impact est.²
	A&T (N=)	Control (N=)	A&T (N=)	Control (N=)		
	Mean (SD)	Mean (SD)	Mean (SD)	Mean (SD)		
Dietary diversity score (number of food groups) Number of IFA tablets consumed						
	Percent	Percent	Percent	Percent		
Minimum dietary diversity (≥5 food groups) Consumed 90+ IFA tablets						

¹Controlling for clusters by health center

² Adjusted for gestational age (PW), maternal age and education, household food security and wealth, and clustering by health center
 *p<0.05, **p<0.01, ***p<0.001

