3.4.2. Analysis of program impact pathways

The program impact pathway (PIP) was developed in collaboration with the A&T program team to map out the mechanisms through which the interventions were expected to achieve impact. The purpose of the PIP analysis is to lay out the theoretical causal links between program activities, outcomes, and impacts. We will examine key indicators along the components of pathways (addressed in part by RQ2

and RQ3), to interpret and support the impact evaluation results. We will compare differences between program groups for indicators along the pathway matched to the relevant outcomes (dietary diversity, IFA consumption, and breastfeeding practices), using linear regression models, accounting for geographic clustering.

Table 7: Measures for program impact pathways

Outcome	Key Indicators	Data source
Service providers' capacity-building and service provision:		
Training and supervision (RQ3)	
 - % NM/HEW received maternal nutrition training - % NM/HEW by training content - % NM/HEW received ANC supervision - % NM/HEW by supervision content 	N-M survey HEW survey
Service providers' knowledge (RQ3)	
 - Knowledge scores for dietary diversity, adequate intake, IFA, and weight gain monitoring - Knowledge scores for breastfeeding 	N-M survey HEW survey
Service provision (RQ3)	
 - % NM/HEW provided maternal nutrition interventions - % NM/HEW by counseling messages provided (on dietary diversity, IFA, weight gain monitoring, and breastfeeding) - % NM/HEW used job aids for maternal nutrition counseling - % HEW provided home visits to PW/number of visits in last 3 months - % HEW conducted PW conference/number of meetings in last 3 months 	N-M survey HEW survey
Beneficiaries' exposure and behavioral determinants:		
ANC visits and contacts (RQ2)	
 - # of ANC visits (at health facility) - % RDW with at least 4 ANC visits - % RDW received ANC visit in first trimester of pregnancy - # of contacts outside of health facility (home visits and GASPA's) 	PW survey RDW survey
Counseling on dietary diversity and adequate intake (RQ2)	
During ANC visits and other ANC contacts:
 
 - % RDW received counseling on maternal nutrition - % RDW received counseling on dietary diversity - % RDW received counseling on consuming adequate quantity of food 	PW survey RDW survey

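### SAP 3.2 tests arm differences in characteristics with a t-test that names no adjustment for health-center clustering, so the starred p-values in Table 5 are wrong, mainly in the endline columns for recently delivered women (minor)

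*SAP*

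**What the plan says.** - SAP 3.2, on maternal, obstetric and household characteristics: "T-test will be used to compare and infer significant difference between the program groups by survey round". Table 5 carries stars at 0.05, 0.01 and 0.001 and has no clustering footnote. SAP 3.1 does not mention clustering either.
- SAP 1.2, on the design: "We applied stratified random allocation to 30 health centers within seven woredas", with 15 centers per arm. Protocol 3.1 adds: "Where there are odd numbers of health centers within woredas, the remaining health centers will be randomized within the same region".
- Protocol 4.4: "Statistical testing for differences between the two groups will be done using a random effects regression, accounting for the clustering of errors".
- Elsewhere the SAP does name clustering. Section 3.3 fits its models "with standard errors clustered at the health center level", both Table 6 footnotes repeat this, and 3.4.2 compares pathway indicators "using linear regression models, accounting for geographic clustering".
- Protocol 2.6 gives the purpose of the small baseline survey: "subsamples of pregnant and recently delivered women will be conducted to assess comparability between study arms".

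**The concern.** An ordinary t-test treats every woman as an independent draw, whereas the arms differ by the allocation of 30 health centers. If women in one catchment resemble each other, the t-test understates the sampling variation of the arm difference and gives stars too easily. Stratification works the other way: variation between regions, and most of the variation between woredas, is balanced by design, yet the t-test still counts it as noise.

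Because the SAP names clustering wherever it wants it, an analyst who follows 3.2 literally will run the plain test. Readers of Table 5 could then take ordinary variation between centers for a failure of randomization or for differential recruitment.

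**Working it through.** **How the plan treats clustering elsewhere.** No figure is stated for the Table 5 tests. The sample-size figures in Protocol 2.6 do reproduce, but only with clustering. With 15 clusters per arm, 28 df, two-sided 5% and 80% power, the detectable difference is (2.048 + 0.855) × SD × √(2V/n), where V = 1 + (m − 1) × ICC and m is women per center.
- IFA tablets: V = 1 + 62 × 0.15 = 10.3; 2.903 × 30.36 × √(2 × 10.3/945) = 13.01, against 13 stated.
- Food groups, ICC 0.21: V = 4.57; 2.903 × 1.39 × √(2 × 4.57/270) = 0.742, against 0.75.
- Food groups, ICC 0.096: V = 2.63; 2.903 × 1.49 × √(2 × 2.63/270) = 0.604, against 0.61.

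**Inputs for Table 5.** Women per center follow from Protocol 2.7 (three kebeles): RDW 3 × 21 = 63 at endline and 3 × 4 = 12 at baseline; PW 3 × 6 = 18 and 3 × 2 = 6. The fallback recruitment for RDW also gives 3 × 10 + 33 = 63. Woreda strata of 3, 2, 5, 7, 5, 4 and 4 centers come from Protocol Table 1. The ICC (0.01-0.05) and the share of it lying between woredas are assumptions.

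**Clustering entirely within woredas.** The true error of the nominal 5% t-test is 2[1 − Φ(1.96/√V)]. For m = 63 and ICC 0.05, V = 1 + 62 × 0.05 = 4.10 and the error is 33.3%.

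**Some or all clustering between woredas.** This needs simulation: stratified allocation, leftover centers of odd-sized woredas randomized within region, 15 centers per arm (5:5 Somali, 10:10 SNNPR), equal center sizes and no true arm difference.

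True error (%) of the nominal 5% t-test, by share of the ICC between woredas:

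| Sample | m | None (formula), ICC 0.01 / 0.02 / 0.05 | Half, ICC 0.01 / 0.02 / 0.05 | All, ICC 0.02 / 0.05 |
|---|---|---|---|---|
| RDW endline | 63 | 12.4 / 19.0 / 33.3 | about 9 / 13.1 / 23.7 | 6.7 / 9.5 |
| PW endline | 18 | 7.0 / 9.0 / 15.0 | about 6 / 7.3 / 10.2 | 5.4 / 5.8 |
| RDW baseline | 12 | 6.3 / 7.6 / 11.5 | about 5.4 / 6.4 / 8.5 | 5.0 / 5.4 |
| PW baseline | 6 | 5.6 / 6.2 / 8.0 | about 5.3 / 5.6 / 6.5 | 5.0 / 5.1 |

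At the three-star level (nominal 0.1%), endline RDW at half share gives 1.2% (ICC 0.02) and 4.7% (ICC 0.05).

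**A characteristic that differs by region only.** Protocol 2.1 reports 38% pastoral in Somali and under 1% in SNNPR. As an illustration, apply 38% and 1% to 10 and 20 centers.
- Overall proportion: (10 × 0.38 + 20 × 0.01)/30 = 0.133. Total variance: 0.133 × 0.867 = 0.1156.
- Variance within regions: (10 × 0.38 × 0.62 + 20 × 0.01 × 0.99)/30 = 0.0851. The ratio is 0.0851/0.1156 = 0.737.
- The arms hold the same mix of regions, so only the within-region part varies, while the t-test uses the total. Rejection is about 2[1 − Φ(1.96/√0.737)] = 2.2%. Simulation gives about 2.0-2.5% across the four samples.

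With a weak regional contrast (ICC 0.02-0.05), simulated rejection is 4.8-5.0%.

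**Candidate replacements, same simulations, nominal 5%.**
- Regression of the 30 center values on arm and seven woreda terms (30 − 1 − 7 = 22 df): 4.7-5.4%.
- Random effects regression with woreda terms: 3.9-6.4%.
- Clustered standard errors on arm alone, endline RDW: 5.4-5.6% with no woreda share, 2.5-3.2% at half, 0.4-1.2% at full.
- Clustered standard errors with woreda terms and the default correction: 8.3-9.2%.

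**The case against.** The strongest reply is that little depends on Table 5, and this stands. No impact estimate, outcome test or sample size uses these t-tests.

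The comparability purpose in Protocol 2.6 belongs to the baseline subsamples, where inflation is slight; the large figures come from the endline RDW sample, to which no passage gives that role. This also stands. So does the point that the size rests on assumed ICCs: near 0.01, three of the four samples are close to nominal.

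It can be argued that Protocol 4.4 is about outcomes and does not mention descriptive tables, and that the SAP itself moves from random effects to clustered standard errors. That weakens any charge of a clear breach. Still, the sentence in 4.4 covers testing between the two groups without exception, and both approaches account for clustering, which 3.2 does not.

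A reader might infer more than the documents support:
- That the impact results are compromised. They are not, since SAP 3.3 clusters by health center.
- That Table 5 chooses the adjustment covariates. SAP 3.3 allows for other variables that may differ between arms, and Protocol 4.4 speaks of analysis to "control for (any) differences at baseline and between intervention and comparison groups for all relevant variables of interest", but neither ties the choice to Table 5 significance.
- That every Table 5 p-value is too small. A strongly regional characteristic errs the other way.
- That the number of false stars can be predicted by multiplying one error rate by the number of characteristics. That gives age, religion and livelihood the same assumed ICC, without documentary support.
- That the outcome ICCs of 0.096 to 0.21 apply to age, education or religion. The documents do not say so.

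**Conclusion.** The point holds as a minor one. As written, the Table 5 test ignores both the unit of randomization and the strata, so its p-values are wrong in a direction that depends on the characteristic. Under the assumed ICC of 0.01-0.05 with half of it between woredas, the inflation is material mainly for endline RDW (about 9-24% at nominal 5%), moderate for endline PW (6-10%) and slight at baseline (5.3-8.5%). If all clustering lies between woredas, endline RDW falls to 6.7-9.5% for ICC 0.02-0.05.

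That the plan omits the adjustment is certain. The size is conditional on the ICC, the woreda share, equal center sizes and the seven strata of Protocol Table 1. The harm is limited to how Table 5 is read.

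**What to change.** In SAP 3.2, do one of two things.

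1. Remove the tests and stars from Table 5 and report standardised differences. This needs no model.
2. Replace the t-test with a test that accounts for health centers and woreda strata. Suitable choices are a regression of the 30 health-center values on arm and woreda (22 df), or a random effects regression as in Protocol 4.4 with woreda terms added (4.4 itself names none).

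If the clustered standard errors of SAP 3.3 are carried over with woreda terms, apply a small-sample correction for 30 clusters. On arm alone they are conservative when woredas differ. A sentence stating that Table 5 significance does not select covariates would also prevent misreading.

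The cost is one or two sentences and the matching Stata command, with no new data.
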